If within routine clinical practice, data will be collected from a follow-up visit approximately one month after end of treatment. Typical information to be collected at this follow-up visit after treatment includes:

- Date of visit
- Patient questionnaires on pain (BPI-SF) and QoL (FACT-BP) filled out by the patient
- WHO pain score
- ECOG status
- Changes in pain medication
- Changes in anti-cancer therapy
- Bone Scan, if available
- Laboratory parameters including ALP, PSA, and blood counts
- Adverse events up to 30 days after last treatment
- Symptomatic skeletal events

Long-term follow-up

For long term follow-up either the patient or treating physician can be contacted by phone, mail or email every three months after end of treatment until death, patient's withdrawal, loss to follow-up, or end of study (whatever comes first in time) for a maximum of two years. Typical information to be collected at long-term follow-up includes:

- Date of follow-up
- Survival status
- Opioid use after last administration of Radium-223 yes/no, if yes, date of first use (only in patients without prior opioid use)
- Symptomatic skeletal events
- Further anti-cancer therapy

End of Observation

The reason for end of observation is documented which could occur at end of study, if the patient died, withdrew his consent or is lost to follow up. In case of death date of death and primary cause of death have to be documented.

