9.3.1 Variables to determine the primary endpoint(s)

The variables for primary objectives are:

- Pain severity will be measured using the worst pain score of the BPI-SF questionnaire. The BPI-SF will be administered prior to each injection of Radium-223 and, if within routine clinical practice, at a follow-up visit approximately one month after the last injection of Radium-223.

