9.5 Study Size

Aim of the sample size consideration is to assess the precision of the estimate for the pain response rate (the primary outcome) which is defined by the width of the 95% confidence interval with a given sample size. Assuming that at least 70% of patients will be evaluable for the primary analysis of pain response at a post-baseline assessment and 30% to 70% of patients show a pain response, at least 300 patients have to be included to reach a precision of < 20%. In the following table, the different scenarios are shown for actual pain response ranging from 30% to 70%.

Table 3: Width of the 95% CI for the pain response rate, assuming 210 evaluable patients

Actual pain response	Lower Limit of 95% CI	Upper Limit of 95% CI	Width of 95% CI
0.7	0.638	0.762	0.124
0.65	0.585	0.715	0.13
0.6	0.534	0.666	0.132
0.55	0.483	0.617	0.134
0.5	0.432	0.568	0.136
0.45	0.383	0.517	0.134
0.4	0.334	0.466	0.132
0.35	0.285	0.415	0.13
0.3	0.238	0.362	0.124

300 patients is a realistic estimate to be enrolled in a two-year enrollment period, based on current patient numbers and available sites for the treatment. With this sample size and a pain response rate of 65% a precision of < 20 % can be reached assuming subgroups to be at least of 1/2 of this size (i.e. 105 patients). From a clinical point of view, this precision is regarded as meaningful, taking the variance of pain measurements into account.

Calculations were performed with nQuery 7.

The sample size could be increased if the number of patients not evaluable for pain response proves to be higher than the expected 30%.

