9.7 Data analysis

9.7.1 Statistical considerations

Statistical analyses will be primarily of explorative and descriptive nature.

All statistical details including calculated variables and proposed format and content of tables will be detailed in the Statistical Analysis Plan (SAP). The SAP will be finalized before study database lock. The SAP is available upon request (see Table 4: List of stand-alone documents, Annex 1).

Patients receiving at least one dose of Radium-223 will be considered valid for safety analysis set.

Analyses of pain or QoL will be performed for patients with evaluable patient questionnaires (BPI-SF, FACT-BP, respectively) at baseline and at least one post baseline visit. A clinically increase or decrease in opioid use will be taken into account. E. g. all patients without opioid intake as well as patients taking opioids will be included in analyses until an increase in opioid intake. Further details will be defined in the SAP.

Other analyses will be performed for the safety analysis set unless otherwise defined.

Whenever reasonable, data will be stratified by subgroups (i.e. age, other baseline characteristics).

All therapies documented will be coded using the World Health Organization – Drug Dictionary (WHO-DD). Medical history, any diseases and AEs will be coded using the latest Medical Dictionary for Regulatory Activities (MedDRA) version.

It is planned to have one interim analysis at the time of 6 months after LPFV. This analysis will use uncleaned data and will primarily focus on pain and QoL assessment. The final analysis will be performed after end of the study which is the date the analytical dataset is completely available.

9.7.2 Analysis of demography, disease details, prior and concomitant medication and other baseline data

Demography and baseline characteristics will be described with summary statistics. Concomitant medication will be coded using WHO's drug dictionary.

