9.7.4 Analysis of primary outcome(s)

The primary analysis of pain response will be summarized in the population of patients with a score >1 (0="no pain") for the baseline measurement of the 'Worst Pain'-item of the BPI-SF. For each post-baseline assessment, the incidence proportion will be provided, along with the exact 95% confidence

interval. Pain response is defined as an improvement of two points from the baseline BPI-SF worst pain score at any post-baseline assessment, which is considered clinically meaningful [17].

Further details will be given in the SAP.

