9.7.5 Analysis of secondary outcome(s)

- Change of pain over time: The responses to each of the BPI-SF items and the following two dimensions which are aggregated from BPI-SF items will be summarized descriptively:
 - Pain severity index:

It uses the sum of the four items on the pain intensity. All four severity items must be completed for aggregating the pain severity index.
 - Pain interference index:

It uses the sum of the seven pain interference items. The pain interference index is scored as the mean of the item scores multiplied by seven, given that at least four of the seven items have been completed.

Summary statistics, including mean and change from baseline, will be provided for each assessment time point. For the summary of each post-baseline assessment, patients will be excluded if there is no corresponding post-baseline measurement.

- For bone pain related quality of life assessment summary statistics including mean and change from baseline will be provided for each assessment time point of the FACT-BP questionnaire. For the summary of each post-baseline assessment, patients will be excluded if there is no corresponding post-baseline measurement.
- Pain control rate will be summarized. Pain control is defined as no increase by two or more points from the baseline measurement of the ‘Worst Pain’-item of the BPI-SF (Question 3) at any post-baseline assessment.
- Pain progression rate will be summarized. Pain progression is defined as two or more points increase from the baseline measurement of the ‘Worst Pain’-item of the BPI-SF (Question 3) at any post-baseline assessment.
- Time to first pain progression will be summarized by Kaplan-Meier (KM) estimates.
- Pain response will be additionally summarized descriptively for the subgroups defined in ‘evaluation of covariates on pain response’ in Section 9.1.2.

An analysis of covariance model will be used to assess changes in pain severity, as measured by the worst pain score on the BPI-SF, at each post-baseline assessment time point. The baseline worst pain score will be used as a covariate in each analysis of covariance model.

- The relation between bone uptake in known lesions and pain palliation will be analyzed (only in patients with bone scan prior to start of treatment and at least one further documented bone scan during or after end of Radium-223 treatment).

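### The pain response rate and the visit-wise pain results leave out patients with no later questionnaire and may be too favourable; a rate counting them as non-responders should stand beside them.

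*Protocol*

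**What the plan says.** Section 9.7.1 sets the population for all pain and quality-of-life analyses: "patients with evaluable patient questionnaires (BPI-SF, FACT-BP, respectively) at baseline and at least one post baseline visit". Section 9.7.4 narrows it, for the primary analysis, to patients whose baseline worst pain score exceeds 1. It defines response as an "improvement of two points from the baseline BPI-SF worst pain score at any post-baseline assessment".

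Section 9.3.1 fixes when a score can exist: "The BPI-SF will be administered prior to each injection of Radium-223 and, if within routine clinical practice, at a follow-up visit" about a month after the last injection. Section 9.2.7 confirms that this last visit is optional: "If within routine clinical practice, data will be collected from a follow-up visit approximately one month after end of treatment". The long-term follow-up listed in 9.2.7 and in Table 2 collects survival, opioid use, skeletal events and further therapy, but no questionnaire.

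For the secondary results, 9.7.5 states: "For the summary of each post-baseline assessment, patients will be excluded if there is no corresponding post-baseline measurement". It also plans a separate analysis of covariance of worst pain at each time point: "The baseline worst pain score will be used as a covariate in each analysis of covariance model".

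The sample size in 9.5 rests on this premise: "Assuming that at least 70% of patients will be evaluable for the primary analysis of pain response at a post-baseline assessment". If more than 30% prove not evaluable, the stated response is to enrol more patients. Section 9.7.8 names loss to follow-up as a source of bias but attaches no analysis to it. Section 9.8.1 and Annex 2 refer missing data to the Data Management Plan.

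**The concern.** The questionnaire schedule follows the injections, so stopping treatment usually ends pain measurement too. A patient who dies, progresses or stops for toxicity after the first injection, and has no follow-up visit a month later, has no post-baseline score. Under 9.7.1 he is then neither a responder nor a non-responder; he is not counted. If such patients respond less often than the others, the reported rate is higher than the rate among the patients who were treated.

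The visit-wise results have the same feature at every step. The mean at a late visit comes from those still being assessed, so a falling mean can reflect who is left as well as what happened to pain.

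This matters for two uses that the protocol names. Section 9.1.3 presents a broad routine-practice population as the strength of the design, and 9.9 expects comparison with historical clinical data. Both depend on knowing which treated patients the rate describes. Enrolling more patients narrows the confidence interval but leaves this selection in place.

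**Working it through.** **Step 1: the plan's own figures.** Evaluable patients: 300 × 0.70 = 210. Table 3 is reproduced by p ± 1.96 × √(p(1−p)/210). At p = 0.50 the half-width is 1.96 × √(0.25/210) = 0.068, giving 0.432 to 0.568 as stated. At p = 0.65 the limits are 0.585 to 0.715, also as stated. The precision figures are right, but they cover only sampling error among evaluable patients.

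**Step 2: who is in the rate.**
- A later questionnaire exists and the patient then stops: counted, because response at any post-baseline assessment qualifies.
- One injection only, follow-up questionnaire completed: counted.
- One injection only, no follow-up questionnaire: not counted.

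**Step 3: effect on the rate.** Let p be the response rate among evaluable patients and m the share of treated patients with baseline worst pain above 1 who lack any later questionnaire. Counting these as non-responders gives p × (1 − m), a drop of p × m.

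| m | Rate when p = 0.50 | Drop |
|---|---|---|
| 10% (assumption) | 0.50 × 0.90 = 45% | 5 points |
| 20% (assumption) | 0.50 × 0.80 = 40% | 10 points |
| 30% (ceiling) | 105/300 = 35% | 15 points |

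At the ceiling, the exact 95% interval moves from 43.0–57.0% (105/210) to 29.6–40.7% (105/300). Over the planned range of p, the ceiling drop runs from 0.30 × 0.30 = 9 points to 0.70 × 0.30 = 21 points. If instead the 90 patients responded at half the observed rate (assumption), 50% would become 0.35 + 0.30 × 0.25 = 42.5%. If all 90 responded, it would become (105 + 90)/300 = 65%.

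The ceiling requires that all 90 non-evaluable patients lack only a later questionnaire. Section 9.5 does not split the 90 by cause. Some may have no usable baseline form or a baseline score of 1 or less, and neither group is in the denominator that defines m.

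**Step 4: visit-wise results.** The number left at the sixth post-baseline assessment is 300 × (1 − d)^6 for a loss of d per visit. For d = 5%, 10% and 15% (assumptions) this is 221, 159 and 113.

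An illustrative simulation shows what selection of this kind can do. Every input is assumed: baseline mean 5, between-patient SD 1.7, random slope SD 0.35 per visit, residual SD 1.3, and essentially no true mean change. The logit of dropout per visit was −2.3 + b × last observed change. With b = 0.3 or 0.5, about half the patients remained at the sixth visit.
- Analysis of covariance at that visit showed a change of about −0.5 to −0.9 points across repeat runs, although the true change was about 0.
- A likelihood repeated-measures model on all visits showed about 0 (−0.07 to +0.04).
- When dropout depended on the current, unseen change instead, that model showed about −0.3 to −0.6. This is less than the analysis of covariance, but not zero.
- With b = 0.1 the analysis of covariance showed only about −0.1, and with no link about 0.

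**The case against.** The strongest reply is that the study is descriptive and concerns pain under treatment. Section 8.1 asks for pain response during radium-223 treatment, and 9.7.1 calls the analyses mainly exploratory and descriptive. A mean among patients assessed at a visit is a legitimate description. A repeated-measures model answers a different question: the mean had everyone kept completing questionnaires, including patients who died. Visits also have no fixed dates. This stands as a reason not to replace the planned analyses. It does not answer the point on the rate, because a descriptive proportion still depends on its denominator.

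A second reply is that further detail is left to the SAP, which was not available for this review and may contain such analyses. That is fair for omissions. Here, however, the evaluable-only rule, the visit-wise exclusion and the separate models are fixed in the protocol itself.

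A third reply is that the questionnaires are paper forms (9.6), so some will be missing for administrative reasons, and scoring those as non-response would understate the rate. This stands, and it is why the added rate should be a sensitivity analysis read together with the reasons for missing forms.

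A reader might also infer that the primary rate describes only patients who stayed on treatment. It does not: one later questionnaire is enough, even if the patient then stops. That description fits the later visit-wise results better, and even these may include the post-treatment visit.

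**Conclusion.** The point holds. The primary rate describes patients who returned at least one later questionnaire, and the visit-wise results describe those assessed at each visit. Because early stopping is plausibly related to pain, both may be too favourable. For an observed 50%, the rate with missing counted as non-response would be 45%, 40% or 35% if 10%, 20% or 30% lacked a later questionnaire. The first two shares are assumptions. The third is a ceiling that takes the whole planned non-evaluable share to be of this kind.

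Three stronger readings are tempting and are not supported. The fall from 50% to 35% is not the expected result of the fix, since the cause of the 30% is not stated. Bias toward benefit is likely on clinical grounds but is not shown by the protocol. A repeated-measures model would not necessarily remove the bias: its near-zero error in the simulation comes from assuming that dropout depends only on observed pain.

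This is an inexpensive improvement that should be made. The planned analyses need not be abandoned.

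**What to change.** In 9.7.1 and 9.7.4, keep the evaluable-only rate. Pre-specify beside it, as the key sensitivity analysis, the response rate among all treated patients with baseline worst pain above 1, counting patients with no post-baseline questionnaire as non-responders. Tabulate missing questionnaires by visit and reason, drawing on the reasons for delay or discontinuation (9.3.6), death and end of observation that are already recorded. Show separately those with no recorded reason.

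In 9.7.5, keep the per-visit analyses of covariance and add one supportive repeated-measures model for worst pain using all available assessments (visit, baseline, baseline-by-visit, unstructured covariance). State that it assumes data missing at random, and that it reduces but may not remove the bias if dropout depends on unobserved pain.

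The cost is wording and some programming; no new data are needed. Precision is not at risk: with 300 in the denominator and the 90 counted as non-responders, the exact 95% interval is at most 0.116 wide for observed rates of 30% to 70%, against the target of less than 0.20. The downside is a second headline rate that is lower, and possibly too low where forms are missing for administrative reasons.

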9.1.1 Primary endpoint(s)

The primary endpoints are:

- **Pain response** as determined by the worst pain item on the BPI-SF patient questionnaire. A clinically meaningful pain response is defined as an improvement of two points from the baseline BPI-SF worst pain score [17] at any post-baseline assessment.

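### The example opioid rule in Protocol 9.7.1 stops using a patient's pain data at an opioid increase, but no pain endpoint counts that increase as a failure

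*Protocol*

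**What the plan says.** Protocol 9.7.1 restricts pain analyses to patients with an evaluable questionnaire "at baseline and at least one post baseline visit". It then says "A clinically increase or decrease in opioid use will be taken into account" and gives one example: "all patients without opioid intake as well as patients taking opioids will be included in analyses until an increase in opioid intake". It closes with "Further details will be defined in the SAP".

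The endpoint definitions contain no opioid component. Pain response is "defined as an improvement of two points from the baseline BPI-SF worst pain score [17] at any post-baseline assessment" (9.1.1, repeated in 9.7.4). Pain progression is a rise of two or more points in worst pain, and pain control is the absence of such a rise (9.1.2, 9.7.5).

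On reporting, 9.7.4 says "For each post-baseline assessment, the incidence proportion will be provided, along with the exact 95% confidence" interval, and 9.7.5 says "Time to first pain progression will be summarized by Kaplan-Meier (KM) estimates". The censoring rules that 9.7.5 leaves to the SAP are attached to next treatment, skeletal events and survival. None is given for pain progression.

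Opioid use appears elsewhere as a covariate for response and, for patients not on opioids at entry, as the endpoint time to first opioid use (9.1.2).

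**The concern.** A patient who needs more opioid has usually had a poor pain outcome. The protocol itself treats opioid need as an outcome: section 7 cites longer time to opioid use as a benefit of the drug, and 9.1.2 makes time to first opioid use an endpoint. Ending a patient's contribution at that event, without scoring it, makes the remaining data depend on how the patient was doing. That is informative exclusion.

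At stake are the per-assessment response proportions reported under the primary analysis, the control and progression rates, and the time-to-progression curve. The study has one arm (9.9), so no comparison group shares and offsets the distortion.

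**Working it through.** **1. The plan's own precision figure.** Section 9.5 takes 70% of 300 = 210 evaluable patients. At 65% response, Table 3 gives limits 0.585 and 0.715, a half-width of 0.065. Check: 1.96 × √(0.65 × 0.35 / 210) = 0.0645. Table 3 reproduces, and the point does not depend on it. It only supplies a yardstick of 6.5 points.

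**2. What the rule does to each endpoint.** The BPI-SF is completed before each injection, typically every four weeks (9.2.7, 9.3.1).

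- *Any-assessment response.* A patient who escalates before the second injection has no usable post-baseline score and leaves the primary set. A patient with one valid score before escalating stays in, as a non-responder if not improved.
- *Per-assessment response.* Everyone who has already escalated is absent from later proportions.
- *Progression and control.* A patient whose scores are cut before a two-point rise is not counted as a progressor.
- *Time to pain progression.* If follow-up ends at escalation, the curve is informatively censored. The protocol does not say whether it does.

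**3. Response arithmetic.** The protocol gives no escalation rate, so every share is assumed. If p is the rate among retained patients and f the share who left through escalation, counting them as non-responders gives p × (1 − f). With p = 65%:

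- f = 5%: 0.65 × 0.95 = 61.8%
- f = 10%: 0.65 × 0.90 = 58.5%
- f = 15%: 0.65 × 0.85 = 55.3%
- f = 20%: 0.65 × 0.80 = 52.0%

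For the any-assessment rate, f covers only escalation before the first post-baseline questionnaire. For a late assessment, f is cumulative: at 30%, 0.65 × 0.70 = 45.5%.

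**4. Progression arithmetic.** Suppose true progression is 40% with escalation counted as an event, and f = 10%, 20% or 30% escalate without an earlier two-point rise (all assumed). If they stay in as non-progressors, the reported rate is 0.40 − f = 30%, 20%, 10%. If they leave the denominator, it is (0.40 − f)/(1 − f) = 33.3%, 25.0%, 14.3%, and control of 60% reads 66.7%, 75.0%, 85.7%. These are upper bounds on the distortion, because no escalator is allowed to progress by score first.

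**5. Direction against two comparators.** An illustrative simulation used six assessments, with every input assumed:

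- baseline worst pain uniform on 2 to 10, plus a patient shift (SD 1.05), a slope per assessment (mean −0.3, SD 0.4) and noise (SD 1.2);
- escalation probability per assessment of 2%, 4% or 6%, tripled when pain is at least one point above baseline and multiplied by 0.3 when it is at least two points below;
- an opioid effect of 0, 1.5 or 2.5 points.

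About 13% to 33% of patients escalated in all, and 3% to 8% before the first assessment.

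| Measure | Rule as written | Escalation counted as failure | All scores used |
|---|---|---|---|
| Response at assessment 6 | 56.8–62.5% | 41.7–49.7% | 54.1–65.3% |
| Progression | 20.9–24.5% | 33.5–45.9% | 20.0–26.3% |
| Response at any assessment | 68.0–71.4% | 62.5–69.5% | 73.3–82.7% |

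Scenario by scenario, the rule exceeds the failure analysis by about 7 to 21 points for response at assessment 6 and by about 2 to 5.5 points for any-assessment response. It understates progression by about 9 to 25 points. Against all scores, it lowers any-assessment response in every scenario.

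**The case against.** The strongest reply is that the sentence is introduced as an example and the details go to the SAP, which could still count an increase as failure. That is correct, and the consequence is not fixed by this document. But the complaint is not about missing detail: the one handling the protocol names is the wrong one. Section 9.7.1 requires the SAP only before database lock. The interim analysis of pain and quality of life is planned for 31 May 2017 and database cleaning for 31 August 2019 (section 6). Nothing in the protocol prevents the rule being settled after single-arm pain results have been seen.

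A reader might infer that every pain rate is flattered and that the rule always favours the drug. The documents do not support that. Patients with a valid score before escalating remain in the any-assessment denominator, and cutting later scores also removes improvements produced by opioids. Nor can one say that opioid-driven relief counts as response: read together, 9.1.1 sets the score criterion and 9.7.1 withholds the scores after the increase. Nor is censoring at escalation stated for time to pain progression; it is only what follows if follow-up is cut there.

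It is also fair that counting escalation as failure is one defensible choice among several in a mainly descriptive study, and that using all scores regardless of opioids is another. The example rule does neither. Separate reporting of time to first opioid use helps only partly, because it covers only patients not on opioids at entry.

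**Conclusion.** The concern holds in a limited form. The example rule in 9.7.1 discards pain data after an opioid increase, and no endpoint definition records the increase as non-response, loss of control or progression. Relative to counting escalation as failure, later per-assessment response and pain control are overstated and progression is understated, by amounts that can exceed the planned 6.5-point half-width. Any-assessment response is affected less, through patients who escalate before their first post-baseline questionnaire.

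Every size given here rests on assumed escalation shares, so the direction relative to that comparator is firmer than any figure. The conclusion also assumes that the example is applied as written; the SAP may provide otherwise.

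**What to change.** Replace the example in 9.7.1 and align 9.1.1, 9.1.2, 9.7.4 and 9.7.5 with it:

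- Patients with a clinically relevant opioid increase stay in the denominator of every pain analysis for which they otherwise qualify.
- They count as non-responders at assessments from the increase onward. A response reached before it stands for the any-assessment rate.
- For pain progression, loss of control and time to first progression, the increase is an event.
- What counts as a clinically relevant increase is defined before the interim analysis of pain data, so that a trivial dose change does not become a progression event.
- The score-only analysis using all data is reported as a sensitivity analysis.

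No new data are needed: 9.3.5 already collects opioid drug, dose, frequency, and start and stop dates. The cost is protocol and SAP wording, a little more analysis work and a somewhat lower headline rate.
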